## **9. Safety**

### **ADVERSE EVENTS INVOLVING DEVICES UNDERGOING CLINICAL INVESTIGATION**

Regulation 16(10)(a) of the Medical Devices Regulations 2002 (SI 618) and Annex X of the Medical Devices Directive 93/42 require manufacturers to record fully all adverse events and report all serious adverse events occurring in all participating centres to the Competent Authority.

A "serious adverse event" is one which:

- a) led to death,
- b) led to serious deterioration in the health of the subject, that either resulted in;
  - 1) a life-threatening illness or injury, or
  - 2) a permanent impairment of a body structure or a body function, or
  - 3) in-patient or prolonged hospitalization, or
  - 4) medical or surgical intervention to prevent life-threatening illness or injury or permanent impairment to a body structure or a body function,

c) led to foetal distress, foetal death or a congenital abnormality or birth defect

NOTE Planned hospitalization for a pre-existing condition, or a procedure required by the CIP, without serious deterioration in health, is not considered a serious adverse event.

All serious adverse events, whether initially considered to be device related or not, involving a device under clinical investigation coming within the scope of the Medical Devices Directive and undergoing clinical investigation, should be reported to the UK Competent Authority (Medical Devices Directive: Annex X, Para 2.3.5 and Active Implantable Medical Devices Directive: Annex 7, Para 2.3.5). Such events also include those arising out of the same investigation being carried out in other countries since such events may have a direct influence on the status of the UK investigation. These reports should initially be made as soon as possible and should not be delayed while the manufacturer attempts to gain access to, or test, the device or make a full investigation. The results of the full investigation should be made available later as appropriate.

MEDDEV 2.7/3 provides guidance on the requirements for reporting serious adverse events with timelines and provides a template form to use for this purpose.

Where an un-blinded controlled clinical investigation is being carried out using a CE marked device as the control, adverse events involving the CE marked devices should be reported to the competent authority in line with vigilance guidelines.

The Competent Authority has the right to withdraw a written notice of no objection if, in its opinion, the serious adverse events give rise to issues of public health (Medical Devices Regulations 2002: Section 16(7) and Section 29(6)).

## **10. Statistics**

This is not a randomised study and there are no comparison or control groups. Outcomes from the study are absolutes as described above. The sample size is comparable to other initial phase CGM studies, is a realistic number for recruitment and provides robust clinical validation and safety data. The study is not powered to show a change in the primary or secondary outcomes compared with usual care but is an assessment of a new technology.

Missing, unused, and spurious data will be assessed on an individual basis and may be ignored, withdrawn or the visit may be removed from the analysis with appropriate justification adjudicated by the Principal Investigator.

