#### **Visit 1:**

- On the morning of the visit, subjects will be instructed to have their standard breakfast and to adhere to their usual practice of diabetes management, this will be maintained throughout study period.
- Attend the Wellcome Trust-Sir John McMichael Clinical Research Facility at the Hammersmith Hospital campus of Imperial College between 9:00 - 10:00 am.
- Between 10:00 – 11:00; subjects will undergo routine clinical examination, have venous blood taken for HbA1c, lipids, creatinine, liver function tests, FBC following an intravenous cannula insertion and female subjects of childbearing age will have a urine pregnancy test performed. This will be followed by insertion of microprobe array and iPro2 device in each subject.
- The outer margin of a 2 cm^2 skin area on the ventral aspect of the non-dominant forearm will be marked before the application of sterile microprobe array to the center of this skin area. The marked skin area will be shaved if hairy. Microprobe insertion will be achieved by applying gentle pressure. Microprobe array will be secured in place using adhesive plaster for 24 hours with 5 minutes sampling as moving average of 1 minute intervals.
- Medtronic iPro2 (Northridge, California) retrospective/blinded continuous glucose monitoring sensor will be implanted in the anterior abdominal wall and calibrated as per manufacturer's instructions.
- An 18-G intravenous cannula will be inserted in the non-dominant upper limb for venous sampling. 2.5 mL venous blood will be taken at 30 minutes intervals between 11:00 - 22:00 the at 60 minutes intervals between 22:00 – 7:00 then back to 30 minutes intervals between 7:00 – 11:00. Venous blood samples will be distributed for venous blood glucose using YSI analyser. Thus, in total, 40 venous samples will be withdrawn from each subject. Maximum blood volume collected over study visit duration is 100mL.
- A 60g CHO meal will be provided between 12:00 – 13:00.
- A 20 g CHO snack will be provided between 15:00 – 16:00 (optional).
- A 60 g CHO meal will be provided between 18:00 – 19:00.
- A 20 g CHO snack will be provided between 22:00 – 23:00 before sleep (optional).
- A 40 g CHO meal will be provided between 7:00 – 8:00.
- At 11:00, devices and intravenous catheter will be removed.

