## 6. Methodology

Non-randomised open label study

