### **20. Study Management**

The day-to-day management of the study will be coordinated by [name]. Weekly research meetings and monthly data reviews will be chaired by the chief investigator or other senior researcher. Annual reports to the funder and sponsor will be written and submitted. The management team will meet at the conclusion of each visit cycle to review data and ensure that no events have occurred requiring progression to the cycle to be halted. The management team will meet again prior to commencing the next visit cycle to ensure appropriate action is taken to mitigate risk of further events. The management team includes a lay member with diabetes and a consultant diabetologist not involved with the study. A community advisory group has been established together with the local Diabetes Research Network to assist in project management. It consists of eight patients with type 1 diabetes, their family members and

carers. The steering group meets every three months to manage the research project, discuss progress and provide guidance and advice to the research group from a patient perspective

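### Section 10 lets the Principal Investigator drop readings or whole visits case by case, with no preset criterion and no masking to the reference, which can inflate sensor agreement.

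*Protocol*

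**What the plan says.** Protocol section 10 (Statistics) sets the exclusion rule in one sentence. It opens with "Missing, unused, and spurious data will be assessed on an individual basis" and goes on to say that such data "may be ignored, withdrawn or the visit may be removed from the analysis with appropriate justification adjudicated by the Principal Investigator". The same section states that "there are no comparison or control groups", and section 6 describes a "Non-randomised open label study".

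The outcomes the rule acts on are in section 5:

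- **Phase 3 primary:** correlation with venous glucose and with iPro2.
- **Phase 4 primary:** correlation with iPro2.
- **Secondary:** the Clarke error grid in all four phases, and a detectable signal in Phase 1.
- **Phase 4 purpose:** sensor lifetime is named here, but it is not a listed outcome.

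Section 11 has the research team, including the engineers, analyse the data.

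**The concern.** A reading that disagrees sharply with YSI or iPro2 is the one most likely to look spurious. If the adjudicator can see the reference, the decision to exclude can depend on the very disagreement that the study measures. Removing whole visits is the stronger form, because a sensor that fails for a day can disappear from the accuracy result altogether.

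Correlation and Clarke zone shares could then describe the sensor only where it worked, yet be read as its accuracy. Phase 1 signal detection and any statement about lifetime are exposed in the same way if visits with failed sensors are removed. No bad faith is needed: case-by-case judgement with the reference in view is enough.

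**Working it through.** **1. Does any other section close the gap?**

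- Section 5, Phase 3, Visit 1 calls the iPro2 a "retrospective/blinded continuous glucose monitoring sensor". That describes the device during wear. It does not mask its values when data are cleaned.
- Section 20 has the management team, which includes "a consultant diabetologist not involved with the study", meet after each visit cycle to "review data and ensure that no events have occurred requiring progression to the cycle to be halted". It also provides for weekly meetings and monthly data reviews. None of these is given a role in exclusions.
- Section 12 opens source data to audit. An all-data result could therefore be rebuilt, but nothing requires it, or a list of exclusions, to be reported.

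**2. Inputs from the protocol.** Phase 3 has 20 subjects, and "in total, 40 venous samples will be withdrawn from each subject". The count reproduces: 23 half-hourly (11:00 to 22:00) + 9 hourly (to 07:00) + 8 half-hourly (to 11:00) = 40. That gives 20 × 40 = 800 sensor–YSI pairs at most. The protocol states no failure rate, no sensor error and no way of pooling the correlation, so everything below is illustrative.

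**3. Main simulation** (600 replicates per setting). Assumptions:

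- Glucose is lognormal around 8.5 mmol/L, with log SD 0.38 within and 0.1 between subjects.
- Sensor error is multiplicative.
- A failed sensor gives independent glucose-like noise or a flat 8.5 mmol/L.
- Zone A means within 20% of the reference, or both values below 3.9 mmol/L.

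Results for a 20% CV with 2 of 20 sensors failed:

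| Measure | All data (noise / flat) | Failed visits removed |
|---|---|---|
| Pooled r, failed for whole visit | 0.804 / 0.838 | 0.884 |
| Pooled r, failed from halfway | 0.844 / 0.861 | 0.884 |
| Zone A, whole visit | 64.7% / 65.8% | 68.7% |
| Zone A, from halfway | 66.7% / 67.3% | 68.7% |
| Mean per-subject r, whole visit | 0.786 / 0.875* | 0.874 / 0.875 |
| Mean per-subject r, from halfway | 0.832 / 0.848 | 0.874 / 0.875 |

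*r is undefined for a flat sensor, so that sensor is left out and nothing changes.

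The whole-visit gain in pooled r is 0.884 − 0.804 = 0.080 (noise) or 0.884 − 0.838 = 0.046 (flat). A hand check on the per-subject figure: a pure-noise sensor has expected r of 0, so (18 × 0.874 + 2 × 0)/20 = 0.787, against 0.786 simulated.

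Range for pooled r, whole visit failed:

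| Setting | All data (noise / flat) | Failed visits removed |
|---|---|---|
| 1 failed, CV 20% | 0.844 / 0.859 | 0.88 |
| 4 failed, CV 20% | 0.723 / 0.789 | 0.88 |
| 2 failed, CV 15% | 0.842 / 0.881 | 0.930 |
| 2 failed, CV 25% | 0.762 / 0.790 | 0.834 |

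**4. No failed sensors, CV 20%.** Dropping the worst 5% of pairs with sight of the reference moves r from 0.884 to 0.908 and zone A from 68.7% to 72.3%. Dropping a random 5% leaves r at 0.883.

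**5. A second, different model** (1,000 runs per setting). Glucose is autocorrelated with mean 9 and within-subject SD 3.2 mmol/L. Sensor error is additive with SD 1.5 to 3.5 mmol/L, and between-subject bias has SD 0.8 to 1.5 mmol/L.

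- No failures, worst 5% of pairs dropped: r goes from 0.896 to 0.902, 0.777 to 0.803 and 0.669 to 0.721 as sensor error grows. With 10% dropped it reaches 0.909, 0.814 and 0.739.
- 10% of visits uninformative (error SD 1.5), worst 1 to 3 visits removed: 0.810 to 0.845–0.881.
- 15% of visits uninformative (error SD 2.5), worst 1 to 3 visits removed: 0.679 to 0.703–0.727.
- No failures, whole visits removed: r changes by at most about 0.003, although the mean absolute relative difference still falls (for example 28.5% to 25.6% with three visits removed).
- Random 10% of pairs dropped: r is unchanged to within 0.001.

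**6. Phase 1 signal detection (assumed counts, exact 95% limits).** Two of 16 sensors without signal gives 14/16 = 87.5% (61.7 to 98.4). If one of those two visits is removed it reads 14/15 = 93.3% (68.1 to 99.8).

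**The case against.** The strongest reply is that most of this belongs in an SAP, which is not shown. A definition of spurious data, masked review, exclusion listings and sensitivity analyses are often placed there, and section 10 is compatible with an SAP that supplies them all. Section 10 also requires a justification and does not name poor agreement as a ground for removal, so trimming the worst 5% of pairs is an extreme use of the clause. What stands is that the protocol does not stay silent or defer. It states a discretionary rule that reaches whole visits, and a justification given afterwards is not a criterion fixed beforehand.

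A second fair point is that the flat-output contrast does not isolate the defect. A preset signal rule might also drop a flat sensor, and pooled r would again be about 0.88. The difference is that under the fix the failed sensor is still counted as failed, and agreement is shown both ways.

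Third, the effect sizes all rest on assumptions, some settings show almost no change, and the Phase 1 intervals overlap heavily. The study is unpowered, and the protocol sets no correlation or Clarke threshold for success or progression. These points limit the consequence and are accepted. They do not affect the direction of the bias.

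**Conclusion.** The concern holds. The rule as written permits agreement to be calculated after the sensor's failures have been removed, and no other section of the protocol prevents that or requires it to be disclosed.

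The direction is clear under two different models: exclusion guided by the reference, or removal of failed visits, raises agreement, while exclusion unrelated to the reference leaves it unchanged. The size cannot be known from the protocol. With 2 of 20 sensors failed and a 20% CV, the gain in pooled r from removing whole failed visits is about 0.05 to 0.08. It is larger with more failures and about 0.02 from trimming pairs when nothing failed. It is close to zero for r when whole visits are removed and no sensor failed. This should be fixed, because correlation is the primary outcome in Phases 3 and 4.

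**What to change.** Replace the sentence in section 10 with a short paragraph that does three things:

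1. Base the primary agreement analysis on all available sensor–reference pairs. Exclude a reading only for a documented reference fault (such as a failed YSI run) or by a sensor-signal rule fixed in advance and applied without sight of YSI or iPro2 values.
2. Do not remove a visit because the sensor failed. Count a sensor that never gives a signal as not detected. If lifetime is reported, treat signal loss or detachment for device reasons as the end of sensor life, and censor at removal for reasons unrelated to the device, such as participant withdrawal.
3. List every exclusion with its reason, and report agreement with and without the exclusions.

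The cost is one paragraph, a little more analysis and possibly less favourable figures. No extra subjects, visits or data are needed.

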## **11. Data**

During the course of the study visits some data will be stored on laptop computers, not connected to the internet, for later statistical analysis. These data will be coded and non-identifiable. Participant data will be stored in a locked filing cabinet in a secure room in Imperial College Healthcare NHS Trust. Only the research team will have access to the filing cabinet. Electronic data will be stored by subject number only on NHS desktop computers which are in the same locked room. Only the research fellow will have access to the data. Laptop computers may be used during the study for portability and convenience. At

the end of each visit the anonymised data will be transferred immediately to the secure NHS computers and will be deleted from the laptop. Access to NHS computers is only by members of NHS staff with appropriate login privileges.

All data will be stored in an anonymised form by using study numbers for identification of participants. The NHS code of confidentiality will be followed and all activity will meet the requirements of the data protection act.

Only members of the clinical research team and those responsible for direct care will have access to subjects' data during the study. The data generated by the study will be analysed by the research team including the engineering team from Imperial College. The analysis will be on anonymised data and will take place in Imperial College Healthcare NHS Trust and in Imperial College academic buildings, both in the Faculty of Medicine and in the Faculty of Engineering.

## **12. Direct Access to Source Data/Documents**

The investigator(s)/institution(s) will permit trial-related monitoring, audits, IRB/IEC review, and regulatory inspection(s), providing direct access to source data/documents.

## **13. Regulatory Issues**

### ***Clinical Trial authorization***

EC medical device directive (updated 2011) states that products manufactured in-house in a healthcare establishment and undergoing testing for proof of concept are not subject of the provisions of the Medical Devices Regulations provided that the device is being manufactured and used on patients within the sole legal entity. As such, and following confirmation from the MHRA, we are not required to submit a notification of clinical investigation to the MHRA for authorization before starting the project.

### ***Ethics Approval***

A favorable opinion from the Research Ethics Committee – London will be sought before starting the project. . The study must be submitted for Site Specific Assessment (SSA) at each participating NHS Trust. The Chief Investigator will require a copy of the Trust R&D approval letter before accepting participants into the study. The study will be conducted in accordance with the ICH-GCP recommendations for physicians involved in research on human subjects adopted by the 18th World Medical Assembly, Helsinki 1964 and later revisions.

## **14. Consent**

Consent to enter the study must be sought from each participant only after a full explanation has been given, an information leaflet offered and time allowed for consideration. Signed participant consent

should be obtained. The right of the participant to refuse to participate without giving reasons must be respected. After the participant has entered the study the clinician remains free to give alternative treatment to that specified in the protocol at any stage if he/she feels it is in the participant's best interest, but the reasons for doing so should be recorded. In these cases the participants remain within the study for the purposes of follow-up and data analysis. All participants are free to withdraw at any time from the protocol treatment without giving reasons and without prejudicing further treatment.

### **15. Confidentiality**

The Chief Investigator will preserve the confidentiality of participants taking part in the study and is registered under the Data Protection Act.

### **16. Indemnity**

Imperial College London holds negligent harm and non-negligent harm insurance policies which apply to this study.

### **17. Sponsor**

Imperial College London will act as the main Sponsor for this study. Delegated responsibilities will be assigned to the Imperial College Healthcare NHS trust.

### **18. Funding**

The Imperial College NIHR Biomedical Research Centre is funding this study.

### **19. Audits**

The study may be subject to inspection and audit by Imperial College London under their remit as Sponsor and other regulatory bodies to ensure adherence to GCP and the NHS Research Governance Framework for Health and Social Care (2nd edition).

### **20. Study Management**

The day-to-day management of the study will be coordinated by [name]. Weekly research meetings and monthly data reviews will be chaired by the chief investigator or other senior researcher. Annual reports to the funder and sponsor will be written and submitted. The management team will meet at the conclusion of each visit cycle to review data and ensure that no events have occurred requiring progression to the cycle to be halted. The management team will meet again prior to commencing the next visit cycle to ensure appropriate action is taken to mitigate risk of further events. The management team includes a lay member with diabetes and a consultant diabetologist not involved with the study. A community advisory group has been established together with the local Diabetes Research Network to assist in project management. It consists of eight patients with type 1 diabetes, their family members and

carers. The steering group meets every three months to manage the research project, discuss progress and provide guidance and advice to the research group from a patient perspective

## 21. Publication Policy

The study will be registered on the clinicaltrials.gov system and results will be disseminated by peer reviewed scientific journals, internal report, conference presentation and publication on websites. No identifiable personal data will be published. All anthropometry and personal clinical data will be expressed as mean/ median and spread of the population in the study. All participants will be informed of the results by letter at the conclusion of the study and details of any publications that arise from the study will be disseminated to participants.

